4.1.2. Analysis methods

4.1.2.1. Analysis method for efficacy estimand

Unless otherwise specified, the primary endpoint, secondary endpoints, and exploratory endpoints will be analyzed according to the efficacy estimand, which represents the efficacy had participants adhered to the randomized treatment without initiating Lp(a) modifying medications. Considered Lp(a) modifying medications are listed in Table EKBC.4.3. The assessment of efficacy measurements guided by the efficacy estimand will be conducted using the EAS (Section 3).

Table EKBC.4.3. Lp(a) Modifying Medica	tions
--	-------

Category	Medication
Lp(a)-Altering therapies	 statins PCSK9 inhibitors prescription-dose niacin mipomersen testosterone, estrogens, anti-estrogens, progestins, selective estrogen receptor modulators, or growth hormone
Excluded Treatment Medical Devices, and/or Procedures	 lipid apheresis any investigational drug, biological agent, or device other than study provided investigational product

A restricted maximum likelihood-based, mixed-effect model repeated measures (MMRM) analysis will be used to analyze continuous longitudinal endpoints. All the longitudinal observations at each scheduled postbaseline visit will be included in the analysis. The MMRM model will include the fixed class effects of treatment group (LY 10 mg, LY 60 mg, LY 240 mg, and placebo), strata (country and baseline Lp(a) stratum [<275 nmol/L, \geq 275 nmol/L as measured by the apo(a) assay]), visit, and treatment-by-visit interaction, as well as the continuous baseline value. An unstructured covariance structure will be used to model the within-participant errors. Significance tests will be based on LS means and Type III tests. If this analysis fails to converge, the following covariance structures will be tested in order:

- 1. Toeplitz with heterogeneity
- 2. autoregressive with heterogeneity
- 3. compound symmetry with heterogeneous variances
- 4. Toeplitz
- 5. autoregressive, and
- 6. compound symmetry without heterogeneous variances.

The first covariance structure that converges will be used. The Kenward-Roger approximation will be used to estimate denominator degrees of freedom.

If the data does not warrant the MMRM model, then an ANCOVA model with treatment group, strata, and the continuous baseline value will be used to analyze the continuous endpoint. Data for participants with missing values at Week 12 will be imputed using the multiple imputation

method under the MAR assumption. Estimates and standard errors from multiple imputed datasets will be combined using Rubin's rules.

For binary endpoints derived from a continuous variable, the missing value in the underlying continuous variable will be imputed first based on the missing at random assumption (MAR), and then the corresponding binary variable will be derived.

A logistic regression model with treatment group and strata as fixed effects and the continuous baseline value as a covariate will be used to examine the treatment difference with missing endpoints imputed. The unconditional treatment group effect will be assessed by risk difference and relative risk using the marginal standardization method, where the treatment group-specific risk will be derived from the counterfactual risks for each participant that are predicted with the fitted logistic model (Ye et al. 2023). The estimated treatment group-specific risk, risk difference, relative risk, p-value and 95% CI will be presented.

For endpoints involving Lp(a), the Lp(a) strata class effects will be excluded from the above models.

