5.1. Inclusion Criteria

Participants are eligible to be included in the study only if all of the following criteria apply:

Age

1. Participants must be at least 40 years old at the time of signing the informed consent.

Type of Participant and Disease Characteristics

- 2. Participants with $Lp(a) \ge 175$ nmol/L at Visit 1, measured at the central laboratory.
- 3. High risk for cardiovascular events defined as documented coronary artery disease (CAD), stroke, or peripheral artery disease or atherosclerotic cardiovascular disease (ASCVD) risk equivalents (familial hypercholesterolemia or type 2 diabetes).
 - CAD documentation should include at least 1 of the following:
 - a. angiographic evidence of ≥50% stenosis of 1 or more major epicardial coronary arteries
 - b. Coronary Artery Calcification Agatston score on computerized tomography (CT) scan of ≥300
 - c. history of myocardial infarction documented by positive enzymes, and either symptoms of myocardial ischemia, or electrocardiogram (ECG) changes (Thygesen et al. 2012)
 - d. history of coronary revascularization
 - e. evidence of cardiac ischemia on exercise testing or imaging study.
 - Stroke (an acute episode of focal cerebral, spinal, or visual dysfunction caused by infarction of central nervous system tissue) documentation should include CT scan, magnetic resonance imaging, or other visualization method. Transient ischemic attack or embolic stroke (not of atherosclerotic origin) are not qualifying events.
 - Peripheral artery disease documentation should include intermittent claudication with an ankle-brachial index ≤0.90 and/or limb amputation or revascularization due to lower limb ischemia. Thromboangiitis obliterans is not a qualifying event.
- 4. Participants on the following medications according to local practice must be on a stable regimen for at least 4 weeks prior to Visit 1 and expected to remain on a stable regimen through the end of the post-treatment follow-up period:

a. lipid-lowering drugs (e.g., statins, ezetimibe, PCSK9 inhibitors, prescription-dose niacin, fibrates, fish oil, or other products containing omega-3 fatty acids, including over-the-counter [OTC] preparations)

b. testosterone, estrogens, anti-estrogens, progestins, selective estrogen receptor modulators, or growth hormone

Weight

5. Have a body mass index within the range 18.5 to 40 kg/m², inclusive.

Sex and Contraceptive/Barrier Requirements

- 6. Male and/or female

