6.8. Concomitant Therapy

Any medication or vaccine, including OTC or prescription medicines, vitamins, and/or herbal supplements, that the participant is receiving at the time of enrollment or receives during the study must be recorded along with

- reason for use
- dates of administration including start and end dates, and
- dosage information including dose and frequency for concomitant therapy of special interest.

The medical monitor should be contacted if there are any questions regarding concomitant or prior therapy.

Participants on the following medications according to local practice must be on a stable regimen for at least 4 weeks prior to screening and expected to remain on a stable regimen through the end of the post-treatment follow-up period, unless changes need to be made because of AEs:

- lipid-lowering drugs (e.g., statins, ezetimibe, PCSK9 inhibitors, prescription-dose niacin, fibrates, fish oil, or other products containing omega-3 fatty acids, including OTC preparations), and
- testosterone, estrogens, progesterone, growth hormone, or progestins.

7. Discontinuation of Study Intervention and Participant Discontinuation/Withdrawal

Discontinuation of specific sites or of the study as a whole are handled as part of Appendix 10.1.

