
Treatment contrast of interest: *difference in mean percent changes in Lp(a) between LY3473329 and placebo.*

Rationale for estimand: This Phase 2 study aims to study the efficacy of LY3473329 under the ideal condition that all participants adhere to the randomized treatment without initiating other medications known to impact Lp(a) levels.

A similar efficacy estimand will be used for the secondary and exploratory objectives.

Unless specified otherwise, safety assessments will be guided by an estimand comparing safety of LY3473329 doses with placebo irrespective of adherence to study intervention or initiation of new Lp(a) modifying medication, including data collected during the treatment period and safety follow-up.

Secondary estimand

For the primary endpoint, a secondary clinical question of interest is: What is the intervention difference in percent change from baseline in Lp(a) after 12 weeks of study intervention in participants who meet the inclusion criteria regardless of treatment discontinuation for any reason or initiation of other medications known to impact Lp(a) levels?

This question is addressed using the treatment-regimen estimand, which is described by the following attributes:

Population: participants who meet the enrollment criteria. Further details can be found in Section 5 of the study protocol of EKBC.

Endpoint: percent change from baseline to Week 12 in Lp(a).

Treatment condition: the randomized treatment. Further details on study interventions, and concomitant interventions can be found in Section 6 of the study protocol of EKBC.

The intercurrent events "intervention discontinuation for any reason" and "new initiation of any Lp(a) modifying medication" are addressed by the treatment-regimen strategy, and the potential

outcome of interest is the response in the efficacy measurement regardless of whether participants had adhered to the randomized treatment without using such medication.

Population-level summary: mean percent changes in Lp(a).

Treatment contrast of interest: difference in mean percent changes in Lp(a) between LY3473329 and placebo.

Rationale for estimand: this estimand aims to study the efficacy of LY3473329 that reflects the real-life behavior of the target population.

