2.1. Multiplicity Adjustment

Treatment comparisons will be performed for the primary objective at the full significance level of 0.05. No multiplicity adjustments will be made for the analysis of secondary and exploratory objectives.

3. Analysis Sets

This table defines the analysis population and datasets for the purposes of analysis.

Population	Description
Screened	All participants who sign the ICF.
Randomized	All participants who are randomly assigned to a treatment arm.
Efficacy Analysis Set (EAS)	Data obtained during treatment period from all randomly assigned participants who are exposed to at least 1 dose of double-blind study treatment. Excludes data after discontinuation of study drug or initiation of Lp(a) modifying medication.
Full Analysis Set (FAS)	Data obtained during the treatment period from all randomly assigned participants who are exposed to at least 1 dose of intervention, regardless of adherence to intervention or initiation of Lp(a) modifying medication.
Safety Analysis Set (SS)	Data obtained during the treatment period plus safety follow-up from all randomly assigned participants who are exposed to at least 1 dose of intervention, regardless of adherence to intervention or initiation of Lp(a) modifying medication.

Abbreviation: ICF = informed consent form.

4. Statistical Analyses

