4.4.2. Main analytical approach

The secondary study objectives will be analyzed with the efficacy estimand using the analytical approaches specified in Section 4.1.2.1. The clinical measures for secondary endpoints may be log-transformed before statistical analyses, if deemed necessary. Specifically, percent change from baseline to Week 12 for Apo(B) and hsCRP will be analyzed by MMRM model. The proportion of participants achieving Lp(a) < 125 nmol/L at Week 12 will be analyzed by logistic regression model.

For each hypothesis, LY3473329 will be declared superior to placebo if the p-value is less than 0.05.

LY3473329 concentration data will be analyzed using a population PK approach via nonlinear mixed-effects modeling with the NONMEM software. The relationships between LY3473329 dose and/or concentration and efficacy, tolerability, and safety endpoints may be characterized. Additionally, the impact of intrinsic and extrinsic participant factors, such as age, weight, gender, and renal function on PK and/or PD parameters, may be examined as needed.

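### For ApoB and the lipid profile, the efficacy estimand drops data after new Lp(a)-modifying drugs but keeps data after newly started ezetimibe, fibrates or omega-3 products

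*SAP*

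**What the plan says.** The SAP carries one efficacy estimand across its endpoints. Section 1.1 states: "A similar efficacy estimand will be used for the secondary and exploratory objectives". Section 4.1.2.1 makes this the default: "Unless otherwise specified, the primary endpoint, secondary endpoints, and exploratory endpoints will be analyzed according to the efficacy estimand". That covers ApoB, which is secondary, and LDL, HDL, total cholesterol and triglycerides, which are exploratory.

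The estimand has two intercurrent events: stopping study intervention, and newly starting an Lp(a)-modifying medication. The Efficacy Analysis Set (EAS, SAP Section 3) turns them into a data rule: "Excludes data after discontinuation of study drug or initiation of Lp(a) modifying medication". For the meaning of that term, Section 4.1.2.1 says: "Considered Lp(a) modifying medications are listed in Table EKBC.4.3". The table names statins, PCSK9 inhibitors, niacin at prescription dose, mipomersen, a group of hormonal agents, lipid apheresis, and investigational products from outside the study. Ezetimibe, fibrates and fish oil or other omega-3 products are not in it.

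The protocol's own list is wider. Inclusion criterion 4a (Protocol 5.1) requires a stable regimen for participants taking "lipid-lowering drugs (e.g., statins, ezetimibe, PCSK9 inhibitors, prescription-dose niacin, fibrates, fish oil, or other products containing omega-3 fatty acids". Protocol 6.8 repeats these classes and allows an exception: "unless changes need to be made because of AEs".

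On analysis, SAP 4.4.2 says: "Specifically, percent change from baseline to Week 12 for Apo(B) and hsCRP will be analyzed by MMRM model". SAP 4.5 sends the lipid profile through the same model. For the data entering it, Section 4.1.2.1 says: "All the longitudinal observations at each scheduled postbaseline visit will be included in the analysis".

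**The concern.** The list was built around what changes Lp(a), then applied unaltered to endpoints that other drugs may change. For ApoB and LDL, a participant who starts a statin at Week 4 loses the Week 8 and Week 12 values. A participant who starts ezetimibe at Week 4 keeps them, and they are analysed as the response to the randomized arm. A new hormonal agent removes ApoB data, while a new drug that the protocol itself calls lipid-lowering does not. The SAP gives no reason for the difference.

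At stake is the reading of the ApoB and lipid contrasts. The SAP's rationale is to isolate randomized treatment under ideal adherence, and SAP 4.4.2 allows superiority on a secondary endpoint to be declared at p below 0.05. If new starts of the omitted classes differ between arms, part of the contrast reflects those drugs.

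**Working it through.** **1. The plan's own figure.** Completers: 233/7 × 0.9 = 29.96 for 10 mg and 2 × 233/7 × 0.9 = 59.91 for each other arm, against about 30 and 60 stated (Protocol 9.5, SAP 5). With SD 20, the standard error (SE) is 20 × √(1/60 + 1/60) = 3.65 points for 60 versus 60, and 20 × √(1/60 + 1/30) = 4.47 for 30 versus 60. A 60-point difference is 60/3.65 = 16.4 or 60/4.47 = 13.4 SEs, so the stated power above 99% reproduces. It concerns Lp(a) and does not depend on this point. The plan gives no SD, effect or power for ApoB or lipids.

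**2. The two lists side by side.**

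| New start | Lipid-lowering in Protocol 5.1, 4a | In SAP Table EKBC.4.3 | Later ApoB and lipid values in EAS |
|---|---|---|---|
| Statin, PCSK9 inhibitor, niacin | yes | yes | removed |
| Hormonal agent | no (listed under 4b) | yes | removed |
| Ezetimibe | yes | no | kept |
| Fibrate | yes | no | kept |
| Fish oil, other omega-3 | yes | no | kept |

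**3. Does another provision close the gap?**
- The treatment-regimen analysis (SAP 4.1.2.2) is for the primary endpoint only.
- The tipping-point analysis (SAP 4.1.2.1.1) is for Lp(a) only.
- The protocol's efficacy estimand (Section 3) has discontinuation as its only intercurrent event.
- The stable-regimen rule is worded for participants already on these drugs. It does not expressly bar a new start. The SAP itself provides for new starts of other classes in the same rule.

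**4. Size of a bias, if there is one.** Bias in the contrast = (difference between arms in the share newly starting such a drug) × (effect of that drug on the endpoint at Week 12). The documents give neither input. Both ranges are assumptions, and every starter is assumed to show the full effect at Week 12.
- 3% and 15%: 0.03 × 15 = 0.45 points
- 3% and 20%: 0.03 × 20 = 0.60 points
- 10% and 15%: 0.10 × 15 = 1.5 points
- 10% and 20%: 0.10 × 20 = 2.0 points
- equal shares: 0 × effect = 0 points

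On the log scale that SAP 4.1 describes for percent change, the two extremes are exp(0.03 × ln 0.85) − 1 = −0.49% and exp(0.10 × ln 0.80) − 1 = −2.21% in the ratio between arms, so the picture is the same.

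**5. Relative to sampling error.** Borrowing the Lp(a) SD of 20 for ApoB (a further assumption), the range is 0.45/3.65 = 0.12 to 2.0/3.65 = 0.55 SE for 60 versus 60, and 0.45/4.47 = 0.10 to 2.0/4.47 = 0.45 SE for the 10 mg arm. In people, 3% to 10% of 60 is about 2 to 6 participants.

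**The case against.** The estimand, the table and the EAS agree with one another. The SAP asks for the effect without new Lp(a)-modifying drugs and removes exactly that data. A reader might infer that the hypothetical strategy fails for ApoB and lipids. As written it does not: it is applied consistently to a narrower set of events. What stands is that the set was not chosen with these endpoints in view.

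A reader might also infer dilution, because LDL stays higher on placebo and prompts more add-on therapy there. The documents do not support that direction. They report no LDL effect of LY3473329; LDL is an exploratory endpoint, and the stated mechanism is reduced Lp(a) formation. Without an LDL effect, LDL values give no reason for unequal starts. With one, this route would weaken a true effect, not create a false one. Other reasons for starting, such as a change made because of an adverse event, could favour either arm. If an imbalance arose with no true effect, the two-sided error at the 10% and 20% extreme would be 0.085 (SD 20 borrowed), but nothing in the documents points to that.

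The route is also narrow. Lipid panels are drawn at Weeks 4, 8 and 12, but only the first two can prompt a start that changes Week 12. ApoB results are withheld from sites. The lipid panel carries no such note in Protocol 10.2, but a general rule there bars reporting results that could unblind, so it cannot be inferred that sites see these values. Treatment lasts 12 weeks, background therapy is expected to stay stable, and several lipid-lowering classes are already on the list. SAP 6.4 summarises concomitant medication by arm, so a large imbalance could be noticed.

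All of this stands and limits the importance. It does not supply a rule for the omitted classes, and noticing an imbalance after unblinding is not the same as having specified how to handle it.

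**Conclusion.** The point holds, with modest importance. For ApoB and the lipid profile, the efficacy estimand borrows a medication list made for Lp(a), and values after newly started ezetimibe, fibrates or omega-3 products remain in the arm means. The contrast is biased only if such starts differ between arms; the direction is unknown. The range of about 0.5 to 2 percentage points rests wholly on the assumed start rates and effects. That these classes act on ApoB at all is also an assumption, because the protocol says only that they lower lipids. The conclusion does not extend to the primary Lp(a) analysis or to the stated power.

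**What to change.** For ApoB and the lipid profile only, add to the intercurrent events the new initiation of any lipid-lowering class named in Protocol 5.1 criterion 4a, and exclude later values of those endpoints from the EAS. Leave Table EKBC.4.3 as it is for Lp(a). At minimum, pre-specify this exclusion as a sensitivity analysis for ApoB and lipids. Either version should be fixed before unblinding.

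The cost is a short SAP amendment and one additional flag. Concomitant medication is already collected at every clinic visit from screening to Week 12 (Protocol 1.3), so no new data are needed. The downside is a few more missing ApoB and lipid values, which the MMRM would handle under a missing-at-random assumption. No sample size or power figure changes.

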6.3. Measures to Minimize Bias: Randomization and Blinding

All participants will be centrally assigned to randomized study intervention using an Interactive Web-Response System (IWRS). Participants will be stratified by country and baseline Lp(a) (<275 nmol/L, ≥275 nmol/L). Before the study is initiated, the log in information and directions for the IWRS will be provided to each site.

Study intervention will be dispensed at the study visits summarized in SoA.

Returned study intervention should not be re-dispensed to the participants.

This is a double-blind study in which participants are blinded to study intervention. The IWRS will be programmed with blind-breaking instructions. In case of an emergency, the investigator has the sole responsibility for determining if unblinding of a participants' intervention assignment is warranted. Participant safety must always be the first consideration in making such a determination. If the investigator decides that unblinding is warranted, the investigator should make every effort to contact the sponsor prior to unblinding a participant's intervention assignment unless this could delay emergency treatment for the participant. If a participant's intervention assignment is unblinded, the sponsor must be notified immediately within 24 hours of this occurrence. The date and reason that the blind was broken must be recorded.

If an investigator, site personnel performing assessments, or participant is unblinded, the participant may be continued in the study.

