Continuous data will be summarized using the sample size, mean, SD, median, minimum, and maximum. The analysis model to make comparisons among treatment groups relative to continuous measurements assessed over time, in addition to the baseline and end-of-treatment measurements, will be a mixed model for repeated measures (MMRM).

The model terms are

- treatment
- visit
- treatment-by-visit interaction
- baseline-by-visit interaction
- baseline measurement
- baseline Lp(a) stratum (<275 nmol/L, $\ge 275 \text{ nmol/L}$), and
- country or region.

Analysis of covariance (ANCOVA) may be used to make comparisons among treatment groups for continuous measurements with only 1 post-baseline assessment. In this case, ANCOVA will be conducted with available data and missing values will not be imputed in the analysis.

Categorical data

Categorical data will be summarized by sample size, frequency, and percentage. Fisher's exact test will be used to examine the treatment difference in categorical outcomes. Logistic regression may be used to examine the treatment difference in binary efficacy outcomes. The negative binomial regression model may be used for the treatment comparison of discrete count measures if deemed appropriate. Participant-specific random effects may be added to the logistic and the negative binomial regression models if longitudinal measurements are available. Model terms in the longitudinal logistic or negative binomial regression models are the same as in the MMRM.

Other statistical methods may be used, as appropriate, and details will be documented in the SAP.

Handling of missing, unused, and spurious data are addressed prospectively in the overall statistical methods described in the protocol and in the SAP, where appropriate. Adjustments to the planned analyses are described in the final CSR.

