9.5. Sample Size Determination

The sample size calculation is based on the primary efficacy estimand and its endpoint, percent change from baseline at Week 12 in Lp(a).

Approximately 233 participants will be randomly assigned in a 1:2:2:2 ratio to LY3473329 10 mg:60 mg:240 mg:placebo. Assuming a 10% dropout rate, this results in approximately 30 completers for the 10 mg group and 60 completers per arm for the rest of the groups.

Assuming a standard deviation of 20%, and a 2-sided alpha level of 0.05, the completers for each treatment arm will provide >99% power to detect a treatment difference of 60% reduction for the primary endpoint of LY3473329 verses placebo. The sample size was determined appropriate to provide a sufficient amount of safety data.

10. Supporting Documentation and Operational Considerations

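### The SAP's MMRM omits the protocol's baseline-by-visit term, and for Lp(a) endpoints excludes the randomization stratum, while declaring no changes from the protocol

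*SAP*

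**What the plan says.** **Protocol.** Section 9.3.1 gives the MMRM terms as treatment, visit, treatment-by-visit, baseline, "baseline-by-visit interaction", baseline Lp(a) stratum (cut at 275 nmol/L) and country or region. It makes no exception for Lp(a) endpoints. Section 9.3.2 adopts this MMRM as the primary model and lets the SAP add covariates; it does not mention removing any. Section 6.3 stratifies randomization by country and baseline Lp(a). Section 9.3.1 also says that changes to non-principal features of the analysis, with their justification, will be described in the SAP or the clinical study report.

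**SAP.** Section 4.1.2.1 lists treatment, the country and Lp(a) strata, visit and treatment-by-visit, "as well as the continuous baseline value". It has no baseline-by-visit term and does not comment on the omission. At the end of the same section, for endpoints involving Lp(a), "the Lp(a) strata class effects will be excluded from the above models". Country stays in every model, and the stratum stays for ApoB, hsCRP and the other non-Lp(a) endpoints. Section 4.1 defines the stratum by the apo(a) assay and runs each Lp(a) analysis twice, on the apo(a) and the intact Lp(a) assay. Sections 1 and 4.9 both state that there are no changes to the protocol's analyses.

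**The concern.** Two programmers, one working from each document, would fit different primary models, and the SAP tells its reader that they are the same.

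Beyond consistency, each term has a statistical purpose. With a single slope, the Week 12 contrast is adjusted by a value pooled over all visits. If the association with baseline fades over time, that value is too steep for Week 12, and part of the precision bought by the covariate is lost. The stratum is a randomization factor. In the intact-assay analysis it is defined by the other assay, so the continuous intact baseline does not fully stand in for it. That run matters because SAP 4.3.2 requires p < 0.05 on both assays to declare superiority.

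**Working it through.** **1. The plan's own figure.** From Protocol 9.5: "Approximately 233 participants will be randomly assigned in a 1:2:2:2 ratio"; "Assuming a 10% dropout rate"; "Assuming a standard deviation of 20%, and a 2-sided alpha level of 0.05"; ">99% power to detect a treatment difference of 60% reduction".

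- Completers: 233 × 1/7 × 0.9 = 29.96 and 233 × 2/7 × 0.9 = 59.91, which matches 30 and 60. In reverse, 210/0.9 = 233.3.
- 10 mg vs placebo: SE = 20 × √(1/30 + 1/60) = 4.47 points, and 60/4.47 = 13.4 standard errors.
- 60 or 240 mg vs placebo: SE = 20 × √(1/60 + 1/60) = 3.65 points, and 60/3.65 = 16.4 standard errors.

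Power exceeds 99.99%, so the stated figure reproduces. For the 10 mg arm the SD would have to triple to 60 before power fell to 99.4%. An SE change of a few percent cannot matter to the primary test.

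**2. Baseline-by-visit.** The Schedule of Activities has five post-baseline treatment visits for Lp(a) and hsCRP (Weeks 1, 2, 4, 8, 12) and three for ApoB and the lipid panel (Weeks 4, 8, 12). With complete data, randomized arms and unit variance at each visit, the ratio of Week 12 SEs (common slope over visit-specific slopes) is

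√[1 + (b_c − ρ₁₂)² / (1 − ρ₁₂²)],

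where ρ₁₂ is the baseline correlation at Week 12 and b_c is the common slope fitted by generalized least squares under an unstructured covariance. The documents give no visit correlations, so these are assumed: the correlation between times s and t (in weeks) is c + (a − c)·exp(−k|s − t|).

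| a, c, k | ρ at Week 1 → 4 → 12 | SE ratio, 5 visits (hsCRP) | SE ratio, 3 visits (ApoB) |
|---|---|---|---|
| 0.80, 0.80, 0 | 0.80 → 0.80 → 0.80 | 1.000 | 1.000 |
| 0.85, 0.70, 0.10 | 0.84 → 0.80 → 0.75 | 1.004 | 1.001 |
| 0.85, 0.50, 0.10 | 0.82 → 0.73 → 0.61 | 1.018 | 1.005 |
| 0.90, 0.50, 0.10 | 0.86 → 0.77 → 0.62 | 1.027 | 1.007 |
| 0.90, 0.30, 0.10 | 0.84 → 0.70 → 0.48 | 1.049 | 1.013 |
| 0.90, 0, 0.05 | 0.86 → 0.74 → 0.49 | 1.055 | 1.019 |
| 0.95, 0, 0.10 (extreme) | 0.86 → 0.64 → 0.29 | 1.109 | 1.027 |

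Worked example (fourth row, five visits): b_c = 0.805, ρ₁₂ = 0.620; (0.185)²/(1 − 0.385) = 0.055; √1.055 = 1.027.

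For Lp(a), whose within-person variability Protocol 2.2.1 describes as low, take an assumed correlation of about 0.95 at Week 1 falling to about 0.90 at Week 12 (a = 0.955, c = 0.88, k = 0.10). Then b_c = 0.936 and ρ₁₂ = 0.903; (0.034)²/(1 − 0.815) = 0.006, a ratio of 1.003. The effect is negligible.

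**3. The stratum, for Lp(a).** This step simulated 4,000 stratified 1:2:2:2 trials per setting under the null, with 210 completers, comparing 10 mg with placebo by ANCOVA on the log scale and keeping the continuous baseline. Assumptions: SD of log change 0.25, log baseline SD 0.35 truncated at 175 nmol/L, and correlation between the analysed baseline and the apo(a) value of 1 (apo(a) run) or 0.9 (intact run).

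| Extra stratum effect (log units) | Model SE without / with stratum, apo(a) | Same, intact | Type I error without stratum, apo(a) / intact |
|---|---|---|---|
| 0 | 0.998 | 0.999 | 0.055 / 0.048 |
| 0.05 | 1.000 | 1.001 | 0.044 / 0.053 |
| 0.10 | 1.005 | 1.008 | 0.050 / 0.050 |
| 0.20 | 1.025 | 1.035 | 0.045 / 0.042 |

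The Monte Carlo error of a 5% rate is √(0.05 × 0.95/4000) = 0.0034. There is no sign of inflation, and the lowest value, 0.042, errs on the conservative side.

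**The case against.** The strongest reply is that this is a documentation mismatch with almost no statistical consequence. Most of that stands.

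- A reader might infer that both terms were dropped silently. That is true only of baseline-by-visit. The stratum exclusion is stated openly and pre-specified; what is missing is its reason and its listing as a change. Protocol 9.3.1 allows such a change without an amendment.
- A reader might infer that omitting a randomization factor undermines the primary test. It does not. For the apo(a) run the stratum is essentially a coarser copy of the continuous baseline, which stays in the model. The simulated loss is near nil unless the stratum has a sizeable effect of its own, and it is only slightly larger for the intact run.
- A reader might infer that the common slope carries the Week 1 relationship over to Week 12. It is a covariance-weighted pool over visits. In the worked example it is 0.805, between 0.86 at Week 1 and 0.62 at Week 12. Randomization keeps the contrast unbiased either way.
- The biomarker loss rests on assumed correlations and vanishes if the baseline slope is constant. ApoB and lipids, with three visits, are affected less than hsCRP.
- The primary endpoint is also analysed by Week 12 ANCOVA, with its own baseline slope, for the treatment-regimen estimand and in the tipping-point analysis.
- Simply deleting the exclusion sentence would be too broad, because it governs the ANCOVA and logistic models too. A participant at 275 nmol/L must fall by more than 1 − 125/275 = 54.5% to get below 125 nmol/L, so responders in the upper stratum may be sparse.

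None of this explains why the SAP departs from the protocol's primary model and says that it does not.

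**Conclusion.** The point holds as a protocol–SAP inconsistency of minor weight. One term of the protocol's primary MMRM is missing without comment, another is excluded openly but not declared or justified as a change, and the two no-change statements are incorrect on this point.

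The treatment contrast is unbiased, type I error is not inflated, and primary power remains above 99%. The possible cost is Week 12 precision for the repeated biomarkers: about 0 to 3% of the SE for ApoB and 0 to 5.5% for hsCRP. The top of the ApoB range comes from the extreme decay pattern, which would give 10.9% for hsCRP. These figures assume the correlation patterns shown, equal variance across visits and no missing data; none of the correlations comes from the documents. A claim that biomarker precision will certainly be lost, or that the primary conclusion is at risk, goes further than the documents support.

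**What to change.** 1. Restore baseline-by-visit in the SAP 4.1.2.1 MMRM. This costs 4 degrees of freedom for five-visit endpoints (Lp(a), hsCRP) and 2 for three-visit endpoints (ApoB, lipids), out of about 230 participants.
2. For the Lp(a) stratum, choose one: keep the exclusion and list it with its reason in SAP 4.9; or add the apo(a)-based stratum to the Lp(a) MMRM only, at 1 degree of freedom. The second option matters most for the intact-assay run. Do not force the stratum into the logistic model for Lp(a) below 125 nmol/L.
3. Correct the statements in SAP Sections 1 and 4.9 for any departure that remains.

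No change to design, sample size or data collection is needed. The work is one model term, one decision on the stratum and two sentences, settled before unblinding.
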